### **Treatment Period**

This period will begin at the Week 0/Day 1 (Baseline) Visit and will end at the Week 24/Early Termination (ET) Visit. At the Baseline Visit, subjects who meet all the inclusion criteria and none of the exclusion criteria described in Section [5.2](#) will be enrolled into the study and randomized to open-label treatment. During this period of the study, subjects will visit the site at Week 0 (Day 1/Baseline), Week 4, Week 8, Week 12, Week 16, Week 20 and Week 24/ET. A  $\pm$  4 day window is permitted around scheduled study visits. If any visit has to be rescheduled, subsequent visits should follow the original visit date schedule. Visits should take place on the same day of the week as much as possible. At the Week 24 visit, subjects who have completed the study will be offered the opportunity to participate in a separate extension study. For subjects that do not elect to enroll into the extension study, a follow-up phone call will be performed at Week 31.

Safety data will be collected throughout the treatment period and up to 15 weeks after the last dose of risankizumab and/or 7 weeks after the last dose of FUMADERM® provided as study medication in this study. Subjects may discontinue study drug treatment at any time during study participation. Subjects that discontinue the study prior to Week 24 will have an ET visit and complete the procedures outlined in [Appendix C](#) within 2 weeks

[figure not shown]
after the decision to discontinue and preferably prior to the administration of any new therapies.

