### **Definition of Analysis Windows**

All time points and corresponding time windows are defined based on Rx Days.

Analysis windows are constructed using the following algorithm:

- Determine the nominal Rx day for each visit (e.g., Week 4 [4 weeks after Baseline visit] equals Rx Day 29).

- In order to include all post baseline data, the first post-baseline interval starts on the first day after the first dose of study drug (Rx Day 2).
- Determine the window around a specific nominal Rx day by adding or subtracting half of the interval between adjacent visits (e.g., days between Week 4 and Week 8 is 28). The threshold between adjacent visits is determined by splitting the interval evenly between the visits. If the resulting split is between Rx days, then the threshold is determined as the midpoint between the adjacent visits. If the resulting split is on an Rx day, then the threshold is determined as being between that Rx day and the Rx day prior to it (e.g., the split between Week 4 and Week 8 would be between Rx Days 43 and 44).
- If more than one assessment is included in a time window the assessment closest to the nominal day will be used. If there are two observations equidistant to the nominal day, the later one will be used in analyses. If more than one assessment is included on the same day, then the worst assessment on that day will be used in analyses, except those specified in Section 11.0.

For subjects who were randomized and not dosed, the date of randomization will be used for determining window definitions.

The following analysis windows have been specified:

**Table 1. Visit Windows for Analysis of Vital Signs, PASI, BSA Involvement, sPGA, Urinalysis, Targeted Safety Laboratory Testing (ITT/Safety Populations)**

Window Label	Target Day	Interval
Baseline	1	≤ 1
Week 4	29	[2, 43]
Week 8	57	[44, 71]
Week 12	85	[72, 99]
Week 16	113	[100, 127]
Week 20	141	[128, 155]
Week 24	169	[156, 183 a ]

Rx Day calculated relative to first dose date of study drug. For subjects randomized but not dosed, Rx Day calculated relative to Randomization.

Targeted Safety Laboratory Testing includes CBC with differential count (hematology), ALT, AST, gamma-GT, alkaline phosphatase (AP) and serum creatinine.

a. For safety analyses (urinalysis and targeted laboratory testing): The minimum of upper bound and 105 or 7 days after the last dose for risankizumab and FUMADERM®, respectively.

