**Table 2. Visit Windows for Analysis of DLQI, PPASI, PSSI, NAPPA-CLIN, PSS, SF-36, PBI, HADS, PtGA, EQ-5D-5L (ITT Population)**

Window Label	Target Day	Interval
Baseline	1	≤ 1
Week 16	113	[2, 141]
Week 24	169	[142, 197]

Rx Day calculated relative to first dose date of study drug. For subjects randomized but not dosed, Rx Day calculated relative to Randomization.

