### **10.1.3 Missing Data Imputations**

Missing data will be imputed using the following methods for the efficacy analyses:

- Non-Responder Imputation (NRI): the NRI analysis will categorize any subject who has a missing value at a specific visit as a non-responder for that visit. The only exception is when the subject is a responder both before and after a specific visit window, and then the subject will be categorized as a responder for the visit. The NRI will be the primary approach in the analyses of categorical variables.
- Last Observation Carried Forward (LOCF): The LOCF analyses will use the completed evaluation from the previous visit for efficacy measures assessed to impute missing data at later visits. Baseline values will not be carried forward. LOCF will be the primary approach in the analyses of continuous variables, and the secondary approach in the analyses of categorical variables.
- As-Observed Cases (OC): The as-observed analysis will not impute values for missing evaluations, and thus a subject who does not have an evaluation on a scheduled visit will be excluded from the as-observed analysis for that visit. As-observed analysis will be the secondary approach in the analysis of continuous variables.
- Multiple Imputation (MI): The MI will be used as sensitivity approach to impute missing data in the primary endpoint. The variables to be included in the imputation model are listed below. If MI is not applicable due to the nature of our data (e.g., MCMC algorithm does not converge), this analysis will not be performed.

The Multiple Imputation analysis will be carried out in three steps.

- Imputation of missing data. The imputation will be generated for the primary endpoint measurement. The variables to be included in the imputation model are: Baseline disease severity (PASI), Baseline weight, treatment group, prior phototherapy exposure, and PASI measurements at each visit from randomization up to the end of the study. For each endpoint, 20 'complete' datasets will be generated using SAS PROC MI. The imputed

post-baseline measurements will be rounded to the same precision as the observed data before the determination of responder status (PASI 90).

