- Analysis of imputed data sets. A CMH test, stratified by stratification factor, will be used to analyze categorical endpoints in each imputed dataset. Synthesis of imputation and analysis results. SAS PROC MIANALYZE will be used to generate the final inferences of the risk difference between treatment groups.

Of note, subjects who discontinued due to AE of "worsening of disease under study" will be counted as non-responders in all subsequent visits in the NRI and MI analyses, and will have their last observation prior to discontinuation carried forward in the LOCF analyses.

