## **10.3 Secondary Efficacy Analyses**

The secondary endpoints will be analyzed in the ITT Population. The following null hypotheses will be tested using two-sided tests with a type I error of 0.05.

The secondary endpoints are as follows:

- Proportion of subjects with a PASI 50/75/90/100 response at Week 4, 8, 12, 16, 20 and 24.
- Change from baseline in PASI at Week 4, 8, 12, 16, 20 and 24.
- Change from baseline in BSA affected by psoriasis at Week 4, 8, 12, 16, 20 and 24.
- Proportion of subjects with a sPGA of 0 or 1 at Week 4, 8, 12, 16, 20 and 24.
- Proportion of subjects with sPGA of 0 at Week 4, 8, 12, 16, 20 and 24.
- Change from Baseline in PPASI Total Score at Week 16 and 24.
- Change from Baseline in PSSI Total Score at Week 16 and 24.
- Change from Baseline on the NAPPA-CLIN Total Score at Week 16 and 24 (for all subjects and for subjects with NAPPA-CLIN > 0 at baseline).
- Change from Baseline on the NAPSI at Week 16 and 24 (for all subjects and for subjects with NAPSI > 0 at baseline).
- Change from Baseline in Psoriasis Symptom Scale (PSS) total score at Week 16 and 24.
- Proportion of subjects achieving PSS (0) at Week 16 and 24.
- Change from Baseline in DLQI total score at Week 16 and 24.
- Proportion of subject achieving DLQI (0, 1) at Week 16 and 24.
- Change from Baseline in SF-36 PCS and MCS Scores at Week 16 and 24.
- Change from Baseline in PBI at Week 16 and 24
- Change from Baseline on HADS at Week 16 and 24.
- Change from Baseline on PtGA at Week 16 and 24.
- Change from Baseline in EQ-5D-5L Index, EQ-5D Utility Index and VAS at Week 16 and 24.

The order of the secondary endpoints does not reflect a ranking.

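### At Week 16 the As-Observed analysis of the continuous SAP Table 2 endpoints repeats the primary LOCF analysis, because the Week 16 window runs from Rx Day 2 to Rx Day 141

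*SAP*

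**What the plan says.** **Missing data (SAP 10.1.3).**
- LOCF is primary for continuous variables and secondary for categorical ones. It fills a missing visit from the previous one, but "Baseline values will not be carried forward".
- As-Observed is secondary and is planned for continuous variables only: "a subject who does not have an evaluation on a scheduled visit will be excluded from the as-observed analysis for that visit".
- NRI is primary for categorical variables: "the NRI analysis will categorize any subject who has a missing value at a specific visit as a non-responder for that visit", unless the subject responds both before and after that visit.
- A closing note covers subjects who discontinue because of an adverse event of worsening disease. They are non-responders at all later visits under NRI, and they "will have their last observation prior to discontinuation carried forward in the LOCF analyses".

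**Windows (SAP 6.0).** All time points are set by Rx Day. The first post-baseline window opens on Rx Day 2, with the stated aim of including all post-baseline data. If several values fall in one window, the one closest to the target day is used.
- Table 2 covers DLQI, PPASI, PSSI, NAPPA-CLIN, PSS, SF-36, PBI, HADS, PtGA and EQ-5D-5L. It has three time points: Baseline, Week 16 [2, 141] and Week 24 [142, 197].
- Table 1 covers PASI, BSA and sPGA among others. Its Week 4 window is [2, 43] and its Week 16 window is [100, 127].

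**Endpoints (SAP 10.3).** The Table 2 instruments are analysed as change from baseline at Weeks 16 and 24. Two responder endpoints are added: "Proportion of subject achieving DLQI (0, 1) at Week 16 and 24", and PSS (0) at the same visits.

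**Visits (Protocol 5.1).** A plus or minus 4 "day window is permitted around scheduled study visits". A subject who stops early has an ET visit within 2 weeks of the decision to discontinue.

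**The concern.** A secondary As-Observed analysis beside a primary LOCF analysis should show whether the result depends on values from subjects who are no longer attending. At Week 16 it cannot do so for the Table 2 instruments. An ET questionnaire from Day 29, for example, is labelled an observed Week 16 value and enters both analyses alike.

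The same visit is treated differently for other endpoints. Under Table 1 it is a Week 4 visit for sPGA and PASI, so the subject is missing at Week 16 and NRI sets sPGA 0 or 1 to non-response. The DLQI and PSS from that visit count as Week 16 data and can yield a Week 16 response.

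Week 16 is one of only two analysis visits for these endpoints, and Protocol 5.6.2 says the quality-of-life measures address a G-BA request. Early leaving may also be unequal between arms. Protocol 3.0 cites 24% discontinuation for adverse events on FUMADERM in another trial, and under Protocol Table 5 the scheduled FUMADERM dose is still rising until Week 8. No specified summary would show how many Week 16 values come from ET visits.

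**Working it through.** **1. Reproduce the windows.** The midpoint of the Table 2 target days is (113 + 169)/2 = 141, and the upper limit is 169 + 28 = 197. Both match Table 2.

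**2. Widths at Week 16.**
- Table 2: 141 − 2 + 1 = 140 days.
- Table 1: 127 − 100 + 1 = 28 days.
- Protocol visit window: 113 ± 4 is Days 109 to 117, or 9 days.
- Days that are Week 16 under Table 2 but not under Table 1: 140 − 28 = 112.

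**3. Compare the two analyses.** As-Observed takes the in-window value closest to Day 113, or nothing. LOCF takes that same value if there is one. If not, it looks to the previous visit, which is Baseline and is not carried, so it also has nothing.

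To check this, take every pattern of a Week 16 visit (absent, or on day a from 109 to 117) with an ET or Week 24 visit (absent, or on any later day up to 197, starting from Day 2). The worsening rule is left aside.
- No Week 16 visit: 1 + 196 = 197 patterns.
- Week 16 visit on day a: 1 + (197 − a) patterns, which over the nine days gives 9 + 756 = 765.
- Total: 197 + 765 = 962.
- **Week 16: the analyses differ in 0 of 962.**
- Week 24: they differ whenever there is a Week 16 value and nothing in [142, 197]. That is 140 patterns without a Week 16 visit, plus 9 + 252 = 261 with one, so 401 of 962.

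**4. Leavers for worsening.** Suppose such a subject discontinues on Day 35 and has an ET visit on Day 40. As-Observed uses the Day 40 value. The closing note of SAP 10.1.3 points LOCF to the last value before discontinuation. That is Baseline, which the LOCF rule says is not carried. Read literally, LOCF has no value, so the analyses could differ here. The SAP does not settle it.

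**5. Responder endpoints.** For DLQI (0, 1) and PSS (0), a subject with an ET value on Days 2 to 141 is not missing at Week 16, so NRI does not act (leavers for worsening excepted). Each ET value of DLQI 0 or 1 adds 1/55 = 1.8 percentage points to the arm's Week 16 rate.

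**6. Size of what the second analysis would miss.** Assume that m of 55 FUMADERM subjects contribute an ET value from before Day 100, that their mean DLQI improvement is d points smaller than that of on-schedule subjects, and that everyone else has a value on Days 100 to 127. If the on-schedule mean improvement is M, then:
- LOCF mean = M − m × d/55
- As-Observed mean on [100, 127] = M
- gap = m × d/55

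As an upper case, m = 13 follows from 0.24 × 55 = 13.2.

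| m (share of 55) | d = 2 | d = 4 | d = 6 |
|---|---|---|---|
| 5 (9%) | 0.18 | 0.36 | 0.55 |
| 9 (16%) | 0.33 | 0.65 | 0.98 |
| 13 (24%) | 0.47 | 0.95 | 1.42 |

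On the planned Table 2 window the gap is 0 in every cell, the worsening rule aside.

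**The case against.** **The mixing comes from LOCF, and including all data is deliberate.** This largely stands. For a continuous endpoint, a leaver's ET value is the value that ordinary LOCF would carry to Week 16 in any case, and Protocol 8.1.4 specifies LOCF. A reader might infer that Table 2 itself shifts the LOCF mean by the amounts above, or biases it towards risankizumab. The documents do not support that. What is lost is the contrast that the second analysis should provide. It is also generally true that LOCF without baseline carry-forward equals As-Observed in a first post-baseline window. Here that window is 140 days long and carries the Week 16 label.

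**As-Observed may already exclude ET values.** The words about an evaluation on a scheduled visit can be read that way, and the two analyses would then differ. But SAP 6.0 defines every time point by Rx Day and gives As-Observed no window of its own. A reader might infer a flat contradiction between Table 2 and SAP 10.1.3. The text supports only an ambiguity that needs a sentence.

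**NRI does deal with some leavers.** Correct: those who leave for worsening are non-responders whatever they recorded. The statement that NRI does not act is limited to other leavers.

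**The stakes are modest.** Also correct. The secondary endpoints are non-confirmatory (SAP 10.4), and Protocol 5.6.2 ties the G-BA's interest in long-term data to the Week 24 primary endpoint. The 24% comes from another trial, and m and d are assumed. A reader might also infer that ET values are contaminated by new therapy. The protocol prefers ET before new therapy without guaranteeing it. How often the order is reversed is unknown, and this point does not depend on it.

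**Conclusion.** The point holds in a limited form. On the Rx-Day reading of SAP 6.0, the Week 16 As-Observed analysis of the continuous Table 2 endpoints is not a second look at the data: it uses the same values as LOCF, with leavers for worsening as the only possible exception. DLQI (0, 1) and PSS (0) have no As-Observed analysis, but at Week 16 they treat an ET value from before Day 100 as observed, whereas sPGA and PASI from that visit leave Week 16 missing.

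The identity follows from the SAP's rules and needs no assumption about dropout. The 0.18 to 1.42 DLQI points rest wholly on the assumed m and d. They show what the planned check could miss and are not an estimate of bias.

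It would be wrong to extend this to Week 24, where LOCF and As-Observed differ, or to PASI 90 at Week 24, which Table 2 does not govern. The change is inexpensive and worth making before database lock.

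**What to change.** Leave the planned LOCF and NRI results as they are, and before database lock:

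1. Run the Week 16 As-Observed analysis of the continuous Table 2 endpoints on the Table 1 window, Rx Days 100 to 127, and say so in SAP 10.1.3. This also settles what a scheduled visit means there.
2. Add a Week 16 sensitivity table for DLQI (0, 1) and PSS (0) in which subjects with no value on Days 100 to 127 are non-responders.
3. Report by arm how many Week 16 values of the Table 2 instruments come from ET visits, with their range of Rx Days.
4. State what LOCF uses for a subject who leaves for worsening before Week 16, so that the closing note of SAP 10.1.3 agrees with the rule against carrying Baseline.

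The cost is one window row, two added tables and a sentence or two of text. No visit made within the permitted 4 days is lost, since Days 109 to 117 lie inside 100 to 127. The As-Observed analysis would have fewer subjects (about 13 fewer on FUMADERM in the upper case above) and would describe those still attending, so it should stay secondary. This defect does not require a narrower Week 24 window or a count of therapy started after the last dose.

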**Figure 1. Study Design Schematic**

**4.3 Sample Size**

Using a two-sided Chi squared test at level of significance 5%, the sample size of 110 (2 × 55) subjects will provide 94% power assuming response rates of the primary endpoint (PASI 90 at Week 24) of 70% for risankizumab and 35% for FUMADERM®.

These assumptions are in line with what has been observed in recent studies for risankizumab (63/83 (75.9%) at Week 24) and FUMADERM® 61/273 (22.3%) of the subjects achieved PASI 90 at Week 16 in the FUMADERM® arm in the BRIDGE trial.

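### On its natural reading, the multiple-imputation check of PASI 90 fits a normal model to raw PASI and imputes too few responders in both arms; predictive mean matching with a named fallback is a cheap improvement

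*SAP*

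**What the plan says.** SAP 10.2 makes non-responder imputation (NRI) the primary approach for PASI 90 at Week 24, with LOCF and MI as sensitivity analyses. SAP 10.1.3 describes the MI:

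- Model: "The variables to be included in the imputation model are: Baseline disease severity (PASI), Baseline weight, treatment group, prior phototherapy exposure, and PASI measurements", the last taken over all visits through study end. Treatment group is a variable in the model, and no imputation by arm is stated.
- Software: "20 'complete' datasets will be generated using SAS PROC MI". No method statement, transformation, minimum or maximum is given.
- Before the responder cut, the only step is that imputed "post-baseline measurements will be rounded to the same precision as the observed data before the determination of responder status (PASI 90") takes place.
- Failure rule: "If MI is not applicable due to the nature of our data (e.g., MCMC algorithm does not converge), this analysis will not be performed". No replacement is named.

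SAP Appendix A gives the PASI range as 0 to 72. Protocol 5.2.1 requires a baseline PASI above 10.

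**The concern.** A PASI 90 responder has a Week 24 PASI of at most one tenth of baseline. That cut is just over 1.0 for a subject at the entry threshold and 1.8 for a baseline of 18, so it sits immediately above the floor of the scale. Under effective treatment many values lie at or near 0, with a long right tail. A normal distribution fitted to such data puts part of its mass below 0 and too little between 0 and the cut. Rounding corrects neither.

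MI is the only model-based check of the primary result, and the missing data may be material and unequal. Protocol 3.0 reports that 24% of FUMADERM subjects in a cited study discontinued because of adverse events. If the imputed response rates are wrong even when dropout is unrelated to outcome, the check is weak in the setting it should handle best. If it fails to run, the plan drops it.

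**Working it through.** **The plan's own figure.** SAP 4.3 states that "the sample size of 110 (2 × 55) subjects will provide 94% power" at rates "of 70% for risankizumab and 35% for FUMADERM". With d = 0.35, mean rate 0.525 and n = 55:

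- z = [0.35·√55 − 1.960·√(2·0.525·0.475)] / √(0.70·0.30 + 0.35·0.65) = (2.596 − 1.384)/0.661 = 1.83, so power is 96.6% without continuity correction.
- With the correction, n is replaced by (55 − 1/0.35)²/55 = 49.4. Then z = 1.63 and power is 94.8%. The corrected formula needs 54 per arm for 94%.

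The stated figure is reproduced, so 70% and 35% with 55 per arm are used below.

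**Assumptions.** The documents give no PASI standard deviation and no dropout rate for this trial. The simulation assumed:

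- baseline PASI of 10 plus a gamma variable (mean about 18);
- a lognormal residual PASI fraction calibrated to the planned rates, log-SD 1.0, 1.3 or 1.8, with visit correlation 0.85;
- monotone dropout unrelated to outcome, FUMADERM/risankizumab 24%/5% or 35%/10%.

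One scenario used the rates from the studies cited in SAP 4.3, 75.9% for risankizumab and, for the comparator, "61/273 (22.3%) of the subjects achieved PASI 90 at Week 16 in the FUMADERM® arm". Each scenario had 40 trials with 20 imputations.

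**Hand check of the mechanism** (log-SD 1.3, cut 1.8, a normal curve with each arm's own simulated mean and SD):

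- Risankizumab, mean 1.95, SD 3.07: P(below 0) = Φ(−0.64) = 26%; P(at or below 1.8) = Φ(−0.05) = 48%, against a true 70%.
- FUMADERM, mean 5.60, SD 6.91: P(below 0) = Φ(−0.81) = 21%; P(at or below 1.8) = Φ(−0.55) = 29%, against a true 35%.

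No pooling of arms enters here. Skewness and the bound at 0 are enough to produce the error.

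**Simulation of the natural reading** (raw PASI, multivariate normal, treatment as covariate). Entries are FUMADERM / risankizumab in %. The risk difference (RD) is in points, MI against complete data.

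| Scenario | Negative imputed values | Imputed PASI 90 | Assumed true rate | RD, MI vs complete |
|---|---|---|---|---|
| log-SD 1.3, dropout 24/5 | 15.5 / 31.2 | 26.7 / 48.1 | 35 / 70 | 37.1 vs 36.4 (+0.7) |
| log-SD 1.8, dropout 24/5 | 14.2 / 36.9 | 21.6 / 51.0 | 35 / 70 | 39.2 vs 37.4 (+1.8) |
| log-SD 1.0, dropout 24/5 | 13.7 / 28.1 | 28.1 / 50.3 | 35 / 70 | 36.4 vs 35.0 (+1.4) |
| log-SD 1.3, dropout 35/10 | 17.3 / 33.9 | 28.8 / 49.3 | 35 / 70 | 38.4 vs 37.1 (+1.3) |
| log-SD 1.3, dropout 24/5, cited rates | 11.2 / 36.3 | 18.3 / 51.8 | 22.3 / 75.9 | 51.0 vs 50.7 (+0.3) |

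Monte Carlo error on the imputed risankizumab rates is several points, since only about 2 to 5 subjects per trial are imputed. The realised true rate among missing risankizumab subjects varied from 60.5% to 79.3% across rows.

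A second simulation used a sequential normal model with dropout given as risankizumab/FUMADERM. At 5%/27% it gave imputed rates of 54% against 71% and 27% against 34%, with an RD bias of about +1 point. The bias was +2.3 points at 5%/40% and −1.8 points at 15%/15%.

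**Why the arm-level effect is small** (first row):

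- Risankizumab: 5% of 55 is 2.75 subjects. The shortfall against the realised 70.8% is 22.7 points, so 0.62 subject, or 1.1 points on the arm rate.
- FUMADERM: 24% of 55 is 13.2 subjects. The shortfall against the realised 33.9% is 7.2 points, so 0.95 subject, or 1.7 points.
- The two errors largely cancel in the difference.

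**Alternatives:**

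- Setting negatives to 0 changes nothing, because a PASI of 0 is also a PASI 90 response.
- Raw PASI imputed by arm still gave 22-29% negatives and 49-55% imputed response on risankizumab.
- Log-scale imputation by arm, at true rates of 35% and 70%, gave 32-36% and 67-71%. The lognormal data favour this method.
- Predictive mean matching by arm (log-SD 1.3) gave about 36% and 71% with no negative values. In the second simulation its RD bias stayed within ±0.5 point.

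**The case against.** The strongest reply is that the SAP does not commit to a normal model on raw PASI. It lists variables and a procedure, MCMC appears only as an example of a failure, and nothing excludes a transformation or another method. That stands: the model is inferred. But the text as written gives a programmer no instruction to do otherwise.

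A reader might infer that negative scores inflate the response rates. They do not. A negative draw counts as a response, but so would a draw set to 0, and the net error is too few imputed responders. A reader might also blame the pooling of arms. By-arm imputation of raw PASI brings FUMADERM closer (27-33% against 35%) but leaves risankizumab far short, so pooling is secondary.

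The consequence is also modest. The planned difference is 35 points and the MI error is about 2 points or less. In the first table row NRI gave 67.5% and 26.2%, a difference of 41.3 points against 36.4 with complete data, so even this MI lies nearer the complete-data value.

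Some early leavers are not model-imputed. SAP 10.1.3 sets those who discontinue for worsening disease to non-responder, and an early-termination PASI falling in the Week 24 window counts as observed. If MI is dropped, LOCF remains. All of this stands and limits the point to a cheap improvement.

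**Conclusion.** The concern holds in a limited form. Read naturally, SAP 10.1.3 applies a normal model to a skewed score bounded at 0 with its cut near 0, and it imputes too few responders in both arms: about 48-54% against 70% on risankizumab and 22-29% against 35% on FUMADERM. The RD bias is about 2 points or less. It was positive wherever FUMADERM dropout was the higher and negative at equal 15% dropout.

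These sizes rest on assumed PASI distributions, assumed dropout rates, and dropout unrelated to outcome. The direction of the imputed-rate error was the same in every scenario run.

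The documents do not support reading this as a threat to the primary conclusion, because NRI and LOCF do not use the imputation model. Nor does the failure rule leave the primary result unchecked; it removes the only model-based check.

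**What to change.** In SAP 10.1.3:

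- Specify predictive mean matching, using PROC MI with FCS REGPMM, or MONOTONE REGPMM if the missing pattern is monotone. Imputed PASI then stays in the observed range.
- Impute by treatment arm where numbers allow, with a reduced covariate set stated in advance if an arm is too small. At 24% dropout about 42 FUMADERM subjects would have Week 24 data (55 − 13.2). With prior phototherapy capped at 20%, about 11 subjects per arm at most would be in that stratum if it is evenly split.
- Replace the rule that drops the analysis with a named fallback, such as the same method with fewer covariates.

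The cost is a little SAP wording and programming before database lock, with no new data. By-arm models are somewhat less precise in a trial of this size. The gain is in credible imputed response rates; a smaller error in the risk difference is not guaranteed if FUMADERM dropout is heavy.
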